4.2.2.2 Restrictions on diet and life style

No restriction

4.3 TREATMENT COMPLIANCE

BI 836880 must be administered as an intravenous infusion under supervision of the investigator or dedicated clinical personnel.

Compliance may be also be verified by pharmacokinetic assessment. Any discrepancies will be documented in the eCRF by the investigator or designee.

Trial Protocol Page 37 of 99

Proprietary confidential information © 2019 Boehringer Ingelheim International GmbH or one or more of its affiliated companies

5. VARIABLES AND THEIR ASSESSMENT

5.1 TRIAL ENDPOINTS

5.1.1 Primary Endpoint(s)

The primary endpoint to determine the maximum tolerated dose (MTD) based on the number of patients presenting dose limiting toxicity (DLT) using the National Cancer Institute (NCI) Common Terminology Criteria for Adverse Events (CTCAE) V4.03, during the first course (i.e. over the first 3 weeks of treatment) and judged to be related to the study medication.

5.1.2 Secondary Endpoint(s)

• Drug related AEs leading to dose reduction or discontinuation during treatment period

5.2 ASSESSMENT OF EFFICACY

The assessment by the investigator and the local radiologist will be the basis for continuation or discontinuation of the trial in an individual patient (in addition to safety). Tumor assessment will be performed every 6 weeks after start of treatment and at the time points specified in the Flow Chart.

After the interim data base lock, frequency of tumor assessment may be adapted according to local standard of care and in agreement with the sponsor if the patient is deriving clinical benefit (e.g. CR, PR or SD > 6 months).

CT images at baseline should be performed as close as possible to the treatment start and not older than 28 days at start of treatment.

At baseline, the investigator along with the radiologist will record the target (five target lesions maximum and maximum two per organ) and non-target lesions at baseline in the eCRF before the start of treatment. The same method of assessment and the same technique should be used to characterize each reported lesion at baseline and during follow up. Lesions in previously irradiated areas may not be considered measurable at baseline unless the lesions occurred after irradiation. Response will be evaluated according to the response evaluation criteria in solid tumors (RECIST version 1.1 (R09-0262). In the event of a delay, interruption or discontinuation of treatment, tumor assessment should continue to follow the original schedule. The schedule should be followed until progression is observed or until the patient commences further treatment for disease, whichever occurs first.

Results of tumor-specific tumor markers which will be assessed routinely should be documented in the eCRF.

After the interim data base lock, documentation of tumor markers in the e-CRF is no longer required.

5.3 ASSESSMENT OF SAFETY

Dose Limiting Toxicity (DLT)

The following drug-related adverse events will qualify as Dose-Limiting Toxicities:

- CTCAE grade \geq 3 non haematological toxicity except:
 - ➤ Vomiting or diarrhea responding to supporting treatment
 - Fatigue lasting for less than 4 days
 - Transcient Grade 3 infusion reaction (i.e. if infusion- related reaction can be controlled by appropriate medication according to investigator's decision and next infusion will not be delayed for more than two weeks).
 - Any laboratory abnormality, which is considered not clinically relevant by the investigator or resolves spontaneously or can be resolved with appropriate treatment. Clinically relevant abnormalities have to be documented as AE (see Section 5.3.6)
- CTCAE grade 4 neutropenia >7 days or complicated by infection (in case of neutropenia grade 4, close observation of patient is necessary.
- CTCAE grade >3 febrile neutropenia
- CTCAE grade = 4 thrombocytopenia
- CTCAE grade > 3 thrombocytopenia with bleeding
- CTCAE grade > 3 proteinuria (urinary protein > 3.5 g/day)
- Hypertension: increase of diastolic blood pressure (BP) by 15 mmHg confirmed by second measurement or ambulatory blood pressure measurement (when indicated; e.g. white coat effect) which cannot be controlled by hypertensive medication and requires a dose reduction of BI 836880 for further treatment course.
- All related AE leading to an interruption of BI 836880 for more than 14 days until recovery to baseline.

The MTD may be considered reached if the probability that the true DLT rate is in target interval (16%-33%) is sufficiently large (for details see Section 7). The DSB may recommend stopping the dose finding phase after the criterion for MTD is fulfilled.

If the next dose level is recommended by the statistical model, however, the efficacy is considered sufficient at current dose level, the DSB may decide to include additional number of patients at this dose level and declare this dose as RP2D and no further dose escalation will happen.

Based on the overall data after all patients on proposed RP2D have been treated for at least 1 course, the DSB will make a final determination of RP2D.

Page 39 of 99

13 Mar 2019

Trial Protocol Proprietary confidential information © 2019 Boehringer Ingelheim International GmbH or one or more of its affiliated companies

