2.3 BENEFIT-RISK ASSESSMENT

BI 836880 has not been tested in human so far. In the 13-week toxicology study in cynomolgus monkeys, BI 836880 was well tolerated up to the highest tested dose of 60 mg/kg.

Anti-VEGF or anti-VEGF-R antibodies have been largely tested in clinic with a well-defined safety profile. Most commonly reported adverse events with such compounds are fatigue, hypertension, proteinuria, diarrhea and bleeding (epistaxis). Severe adverse events include gastrointestinal perforations, tumor haemorrhage and arterial thromboembolism (R14-3588, R14-3261).

There is less clinical experience with anti-Ang2 compared to VEGF pathway blockade clinical experience. The most advanced anti-angiopoietin compound (Trebananib) in development is in Phase III in combination with chemotherapy (R14-5440). Other anti-Ang2 compounds are currently in early stage of clinical development (R15-1645, R15-1646, R15-1648). From this clinical experience the most commonly reported side effects are fatigue and gastro-intestinal symptoms (diarrhea, nausea and vomiting). No bleeding or thromboembolic events were reported with this class of compound. Of note, almost all tested anti-Ang2 molecules failed to define a MTD (R15-1646, R15-1648).

Limited clinical experience of dual blockade is available. Recently, Phase I data of the bispecific human anti-Ang2/anti VEGF-A antibody (RG7221) were reported. MTD was not reached with only one dose limiting toxicity (DLT) reported (fatal pulmonary hemorrhage). Hypertension was the most common observed adverse event (R15-1644).

Based on this clinical available data it is expected that blockade of both targets will result in similar side effects as anti-VEGF and anti-Ang2 blockade. Based on the phase I trial results of RG7221 no increase in side effect severity is anticipated with BI 836880. It is anticipated that the safety profile of BI 836880 will most likely include fatigue, hypertension, proteinuria, gastro-intestinal side effects and bleeding.

Previous clinical experience with nanobodies in different disease showed acceptable safety profile with no specific side effect related to this technology (R13-2303).

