4.1.4 Drug assignment and administration of doses for each patient

The study drug will be prepared according to "Instruction for Pharmacists" which will be filed in ISF. Upon notification of an entered patient in the study, the pharmacy will prepare the study drug in the assigned dosage for administration to the patient.

BI 836880 will be given as weekly intra-venous infusion by authorised site staff in a specialized unit where emergency care can be provided (e.g. intensive care unit available, medical personal trained in advanced live support) according to "Instruction for Pharmacists". The expected infusion time is 90 min. in case no relevant infusion reactions are observed, this may be shortened to about 30 min but should not be prolonged to more than 6 hours even in case of technical issues. Appropriate drugs and medical equipment to treat anaphylactic reactions must be immediately available and study personal must be trained to recognize and treat anaphylaxis.

If symptoms of an infusion-related reaction CTCAE grade ≥ 2 occur (that are not qualifying as DLT according to Section 5.3), the infusion should be temporarily stopped. Upon recovery, infusion should be resumed at 50% of the rate at which the reaction occurred. Depending on the time of occurrence and the severity of the reaction, the investigator may consider administrating additional supportive medication, e.g. corticosteroids for reintroduction. Infusion rate and premedication for further treatment courses should be adapted according to Investigator decision, but adaptation of application scheme need to be agreed with sponsor.

BI 836880 will be administrated intravenously starting on course1 day1. In the event of delay or interruption of treatment due to adverse event, BI 836880 infusion should be skipped; and the next scheduled BI 836880 infusion should be administrated upon recovery to CTCAE Grade 1.

Premedication: No premedication will be required for BI 836880 IV infusion.

If a patient experienced sign of infusion reaction at any BI 836880 treatment, a premedication will be **considered** for all subsequent treatment infusions (dosage and schedule according to investigator's decision) comparable to the following scheme:

- Acetaminophen/paracetamol 650 mg-1000 mg p.o., or equivalent
- Antihistamine p.o. or i.v., equivalent to Diphenhyldramine 50 mg i.v.
- Glucocorticoid i.v., equivalent to prednisolone 100 mg

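### The vomiting/diarrhoea exception to the DLT definition has no upper grade and no time to response of its own, and the 14-day interruption item only partly closes the gap

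*Protocol*

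**What the plan says.** Protocol Section 5.3 lists the drug-related events that qualify as DLTs. The first item is grade 3 or higher "non haematological toxicity except", followed by four exceptions:

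- "Vomiting or diarrhea responding to supporting treatment": no grade and no time stated.
- "Fatigue lasting for less than 4 days": a duration limit, no grade cap.
- "Transcient Grade 3 infusion reaction": grade 3 only, provided it is controllable and the "next infusion will not be delayed for more than two weeks".
- Laboratory abnormalities that are not clinically relevant, resolve spontaneously or can be resolved with treatment: no grade and no time stated.

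A separate item, outside the exceptions, also makes the following a DLT: "All related AE leading to an interruption of BI 836880 for more than 14 days until recovery to baseline". Section 4.1.4 links adverse events to interruptions: an infusion is skipped, and "the next scheduled BI 836880 infusion should be administrated upon recovery to CTCAE" grade 1.

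Section 5.1.1 restricts the primary endpoint to the first course, three weeks. SAP Section 5.1 takes the DLT definition from protocol Section 5.3 and adds no limit. Protocol Section 2.3 names fatigue and "gastro-intestinal symptoms (diarrhea, nausea and vomiting") as the most commonly reported side effects of anti-Ang2 compounds, and expects gastro-intestinal side effects with BI 836880.

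**The concern.** The exceptions hang on an item that starts at grade 3 and has no ceiling, so an exception without a grade removes grade 4 as well as grade 3. The word describing response carries no deadline and no required end state. Read literally, a drug-related grade 4 diarrhoea that responds and allows dosing to resume within 14 days is scored as tolerated.

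The DLT count is the only data input to the model that sets the overdose limit and the MTD. Cohorts may be as small as two patients, so one event can decide whether the next dose is admissible. Any miscoding runs in one direction: the counted DLT rate goes down and the permitted dose goes up. Vomiting and diarrhoea are also toxicities that the protocol expects for the class, although it gives no grade or frequency for them.

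**Working it through.** **Inputs (protocol Section 7.1).** The model is logit p(d) = log α + β·log(d/1250). The prior on (log α, log β) is a mixture of three normals with zero correlation:

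- weight 0.90, mean (0.740, 0.798), SD (2, 1)
- weight 0.05, mean (0.846, −0.123), SD (2, 1)
- weight 0.05, mean (−2.731, 0.193), SD (5, 0.01)

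With r DLTs in n patients at each dose, the posterior is proportional to prior × Π p(d)^r·(1−p(d))^(n−r). P(OD) is the posterior probability that p(d) is at least 0.33. A dose is admissible if P(OD) is below 0.25. The integration was done numerically on a grid spanning ±7 prior SD for each component.

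**Step 1: reproduce the plan's figures.** P(OD) at the current dose, Table 10.6:1:

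| Scenario | Printed | Recomputed |
|---|---|---|
| 1 | 0.019 | 0.020 |
| 2 | 0.318 | 0.325 |
| 3 | 0.018 | 0.019 |
| 4 | 0.231 | 0.237 |
| 5 | 0.623 | 0.630 |
| 6 | 0.02 | 0.020 |
| 7 | 0.229 | 0.227 |
| 8 | 0.353 | 0.339 |

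The largest difference is 0.014 (scenario 8), so the rebuilt model is adequate for this purpose.

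**Step 2: recode one event.** Each row treats a single event as counted (1/3) or exempted (0/3), everything else fixed:

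| Data so far | Dose assessed | P(OD), counted | P(OD), exempted |
|---|---|---|---|
| three patients at 40 mg | 40 mg | 0.325 | 0.011 |
| same | 120 mg | 0.613 | 0.048 |
| 0/2 at 40 mg, then three at 120 mg | 120 mg | 0.237 | 0.011 |
| same | 150 mg | 0.316 | 0.018 |
| same | 240 mg | 0.510 | 0.049 |
| 0/2, 0/2, 0/3 at 40, 120, 240 mg, then three at 480 mg | 480 mg | 0.227 | 0.020 |
| same | 720 mg | 0.562 | 0.121 |

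The 150 and 720 mg levels come from the current Table 4.1.3:1; Appendix 10.6 does not evaluate them. In all three settings the set of admissible doses changes. After 40 mg it goes from none to 120 mg. After 120 mg it goes from staying at 120 mg to allowing 240 mg. After 480 mg it goes from staying at 480 mg to allowing 720 mg.

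Section 3.1 adds a second effect. A DLT in one of two patients triggers a third patient, and an exempted event does not. Escalation could then rest on 0/2 at 120 mg, where P(OD) at 240 mg is 0.065 (printed 0.066, scenario 3), also admissible.

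**Step 3: test the 14-day backstop against the DLT window.** Nominal infusion days in course 1 are 1, 8 and 15, and the window is 21 days. The protocol does not say when the interruption clock starts.

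- Counted from a missed day-8 infusion: 8 + 14 = 22, so the item is met only after day 22.
- Counted from a missed day-15 infusion: 15 + 14 = 29, so only after day 29.
- Counted from the last infusion given, if that was day 1: 1 + 14 = 15, so after day 15, inside the window.
- Counted from the last infusion given, if that was day 8: 8 + 14 = 22, again outside.

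Whether the backstop reaches the course 1 DLT count therefore depends on an unstated convention. Under none of these readings does it catch a grade 4 event with dosing resumed within 14 days.

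**The case against.** Several points on the other side have force.

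- **There is an outer limit.** A reader might infer that an event may take any length of time to respond and still be exempt. The documents do not support that. An event that keeps the patient off drug for more than 14 days is a DLT in its own right, and Section 4.1.4 ties re-dosing to recovery. What remains is that this limit ignores grade and may act too late for the course 1 count.
- **The scope is narrow.** A reader might infer that severe gastrointestinal toxicity in general is exempt. Only vomiting and diarrhoea are; other drug-related grade 3 or higher gastrointestinal events remain DLTs. Nor do the documents describe what a grade 4 event means clinically; they cite CTCAE.
- **The list has no uniform convention.** Only the infusion-reaction exception has a grade cap, fatigue has a duration limit alone, and the laboratory exception has neither. The contrast is therefore with two of the other three exceptions, not all of them.
- **The arithmetic is generic.** Moving any single DLT to non-DLT would shift the model in this way. It shows sensitivity, not how often this exception would operate, and no rate is given.
- **The model does not set the dose alone.** The DSB decides on all collected safety data and may expand a cohort or choose an intermediate dose. Appendix 10.6 even says that escalation could still happen after DSB discussion when one of three patients has a DLT at 40 mg. So 0.049 at 240 mg means permitted, not that the dose is doubled.

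These points limit the size of the claim. They do not remove it: DSB caution does not correct the DLT count that enters the model and the primary analysis in SAP Section 7.4.

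**Conclusion.** The point holds in a limited form. As written, a drug-related grade 4 vomiting or diarrhoea event that responds, with dosing resumed within 14 days, is coded as no DLT. The 14-day item only partly covers the gap.

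In the settings checked, one such recoding is enough to make a blocked dose admissible. P(OD) goes from 0.51 to 0.049 at 240 mg and from 0.562 to 0.121 at 720 mg, against 0.25. This rests on the model and prior in Section 7.1, three-patient cohorts, and exactly one affected patient.

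The documents do not support a stated bias in the MTD, because they give no frequency for such events and the DSB can decline to escalate. The defect is in the definition of the primary endpoint, so it deserves correction, but it does not by itself invalidate the design.

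**What to change.** In Section 5.3 the sponsor should put an explicit upper grade and an explicit time to response, both of its own choosing, on the vomiting/diarrhoea exception. It should reconcile that wording with the fatigue and infusion-reaction exceptions. For the 14-day interruption item it should state when the clock starts, and whether an interruption that begins in course 1 but passes 14 days after day 21 counts for course 1. No clinical threshold is proposed here.

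The SAP inherits the change through its Section 5.1 reference to protocol Section 5.3. SAP Section 7.4 points instead to protocol Section 5.3.1, which is now the physical examination section, and can be corrected at the same time.

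The text change is short, but it has consequences. A rare event may now count as a DLT and slow escalation slightly. Cohorts have already been treated under this definition (Section 11 records that 150 and 180 mg were tested), so any patient with such an event would need recoding and the model rerunning. DLT status also drives temporary stopping and dose reduction (Section 4.1.4.2), withdrawal (3.3.4.1), eligibility for intra-patient escalation (4.1.3) and reporting as an adverse event of special interest (5.3.6.1), so those rules would follow the new definition.

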5.3.1 Physical examination

A complete physical examination including (height at screening only), cardiac, neurological, dermatological pulmological, weight and ECOG performance score, will be performed at screening and before the start of the treatment, EoT and EoR. At further time points specified in the Flow Chart, not a complete physical examination will be performed, but at minimum the actual health status of the patient should be assessed (including, evaluation of blood pressure, ECG, lab safety parameters, AEs, concomitant therapies, ECOG as applicable). During the physical examination, the patient should be assessed for possible AEs. After the interim data base lock, physical examination, ECOG performance status, weight are no longer mandatory at the specific visits but will be performed at the investigator's discretion. Findings will be documented in the eCRF only if qualifying as (S)AE.

5.3.2 Vital Signs

Vital signs (blood pressure, heart rate and body temperature) will be recorded at every visit indicated in the flow chart.

At day of administration two time points will be evaluated:

- 1- At pre-dose (-60 minutes to 5 minutes)
- 2- Shortly before the end of infusion

In case of an infusion-related reaction, if deemed necessary, the investigator should decide for intensive monitoring of vital signs.

Blood pressure

Systolic and diastolic blood pressure as well as pulse rate (electronic or by palpation, count for 1 minute) will be measured after 5 minutes of rest in seated position. The blood pressure measurement should be performed three times at each time point and values of these measurement will be entered in the CRF (refer to Appendix 10.2 and Appendix 10.4) After the interim data base lock blood pressure is no longer mandatory at specific visits but will be performed at the investigator's discretion. Findings will be documented in the eCRF only if qualifying as (S)AE

Body temperature

Whenever possible the same method should be used for body temperature measurement in one patient. All methods used should deliver valid reproducible results according to common clinical practice.

Body temperature > 38°C must be re assessed 1 hour after, especially in cases of suspected febrile neutropenia (see CTCAE V.4.03).

After the interim data base lock body temperature is no longer mandatory at specific visits but will be performed at the investigator's discretion. Findings will be documented in the eCRF only if qualifying as (S)AE

Page 40 of 99

Proprietary confidential information © 2019 Boehringer Ingelheim International GmbH or one or more of its affiliated companies

5.3.3 Safety laboratory parameters

Blood sample for assessment of safety laboratory examinations have to be collected at the time points specified in the Flow Chart, but should be more frequent in case of relevant findings, e.g. in case of grade 4 neutropenia, as any non-proven recovery within 7 days will be counted as DLT or proteinurea, for which determination of CTCAE grade 2 versus grade 3 needs to be done by quantitative measurement.

Safety laboratory examination will include haematology, biochemistry, coagulation, and urine analysis.

- **Haematology**: Haemoglobin, red blood cell count (RBC), white blood cell count (WBC) and differential, platelets.
- **Biochemistry**: glucose, sodium, potassium, calcium, magnesium, inorganic phosphate, creatinine, aspartate amino transferase (AST), alanine amino transferase (ALT), alkaline phosphatase, lactate deshydrogenase (LDH), bilirubin, urea, total protein, albumin, uric acid, CK, CK-MB.
 - Serum immunoglobulin levels (IgG, IgM, IgA, IgE) and direct antiglobulin test have to be measured at screening and at occurrence of infusion related reactions.
- Coagulation: activated partial thromboplastin time (aPTT), prothrombin time (PT) or international normalised ratio (INR) where indicated (e.g. treatment with vitamin K antagonists)
- Urinalysis: pH, glucose, leukocytes, erythrocytes, protein, nitrite will be analysed primarily qualitatively by dipstick. In case of pathological findings, further evaluation should be performed and the findings documented. A positive urine dipstick for protein of ≥ 2+ has to be followed by a determination of urine protein to creatinine ratio (UPCR) in a morning spot urine sample. In case of a ratio ≥ 0.5, a 24-hour urine collection for protein loss has to be performed. The 24 hour urine collection will be repeated every time the UPCR is ≥ 0.5 as often as clinically indicated.

After the interim data base lock, safety laboratory tests (haematology, biochemistry, coagulation, urinalysis) will be performed at the investigator's discretion based on the standard medical care. Findings will be recorded in the e-CRF only if qualifying for (S)AE/AESI.

Pregnancy test: a serum pregnancy test will be performed as outlined in the Flow Chart in women of childbearing potential.

Previous laboratory investigations performed within 72 hours prior to the first treatment administration visit are acceptable to confirm the patient eligibility.

In case an administration is delayed due to an AE, the patient should visit the site at least once a week for assessment of safety laboratory and AEs. More frequent visits may be appropriate as assessed by the Investigator.

